#### Secondary

- Best response following 3 and 6 cycles of treatment
  - Assessment will be made according to the following criteria:
    - "Proposed criteria for response assessment in patients treated in clinical trials for MPNs in blast phase (MPN-BP): Formal recommendations from the post-MPN acute myeloid leukaemia consortium" (for patients with ≥20% bone marrow blasts at baseline)[1]
    - International Working Group (IWG) response criteria in myelodysplasia (for patients with <20% bone marrow blasts at baseline)[2]

- Change in the proportion of patients who require transfusion of red cells or platelets after completion of cycles 3 and 6
- Achievement of red blood cell (RBC) transfusion independence after completion of cycles 3 and 6.
- Achievement of platelet transfusion independence after completion of cycles 3 and 6.
- Change in palpable splenomegaly or hepatomegaly after completion of cycles 3 and 6.
- Duration of Complete Response (CR) or Partial Response (PR)
- 12 months Progression-free survival (PFS)
- 12 months Leukaemia-free survival (LFS)

- 12 months Overall survival (OS)
- Duration of trial treatment
- Clinical improvement in haemoglobin level
- Clinical improvement in platelet count
- Quality of life as measured by the MPN SAF; EQ-5D-5L and EORTC QLQ-C30 (baseline and cycles 1, 2, 4 and 6)

#### **Observational Component**

- To determine treatment and outcome of Accelerated Phase MPN (MPN-AP) and Blast Phase MPN (MPN-BP) patients who enter the observation component
- Quality of life as measured by the MPN SAF; EQ-5D-5L and EORTC QLQ-C30 (at registration, 3 months and 6 months)

#### Exploratory (both components)

• Change in clonal marker (e.g. JAK2 or CALR allele burden) (to be centrally assessed)

# 3. TRIAL DESIGN

#### 3.1 Interventional Component

This is a single arm, multicentre, phase I dose finding study of ruxolitinib combined with 5-azacitidine in patients with advanced phase MPNs, including MDS or AML arising from MPNs.

The aim of this study is to define the MTD for ruxolitinib in combination with 5-azacitidine using a restricted two-stage Bayesian CRM. The MTD is defined as the dose level with an associated DLT probability over the first cycle of treatment (28 days) that is closest to the target DLT rate of 25%.

The dose levels of ruxolitinib are 5 mg, 10 mg, 15 mg, 20 mg and 25 mg twice daily. 5-azacitidine is given at a fixed dose of 75 mg/m^2 at each dose level. Patients will be assigned to the dose levels in cohorts of up to 5. The prior estimation of MTD is at dose level 3, however to exercise caution, dose level 0 is defined as the starting dose.

In the first stage, the first cohort of 3-5 patients will be enrolled at dose level 0. If none experiences a DLT, the next cohort of 3-5 patients will be recruited at the next level, (i.e. dose level 1). This process continues until the first DLT is observed in a cohort. Once there is a DLT, the second stage which comprises of the model based CRM begins.

In the second stage, the recommended dose for each new cohort of up to 5 patients will be made using the CRM taking into account all the previous data observed including the first stage. This would be the dose with estimated DLT probability closest to the target of 25%. Subsequent cohorts will be assigned a dose level in the same way using all previous data observed until the MTD is declared or the maximum sample size is reached.

See Section 12 on Statistical Considerations for more model details.

Dose Level	Ruxolitinib dose	5-azacitidine dose					
	(oral bi-daily)	(subcutaneously (5, 2, 2))					
Dose -1	5 mg	75 mg/m 					
Dose 0 (starting dose)	10 mg	75 mg/m 					
Dose 1	15 mg	75 mg/m 					
Dose 2	20 mg	75 mg/m 					
Dose 3	25 mg	75 mg/m 					

Table 1: Five dose levels of combination of ruxolitinib and 5-azacitidine

All patients will receive 6 cycles (28 days per cycle) of combination treatment. Following 6 cycles patients may continue to receive study treatment whilst obtaining clinical benefit, in the view of the local investigator. Typically this will be appropriate for patients in CR, PR or exhibiting stable disease.

Once the MTD is declared, patients recruited at a lower dose may receive the MTD for any subsequent cycles of treatment at the discretion of the treating Investigator and the Chief Investigator.

Bone marrow examinations will take place at baseline and after 3 and 6 cycles of treatment or where there is evidence of remission or progression in the peripheral blood (according to Investigator discretion).

# 3.2 Observational Component

Patients who are unwilling or unable to enter the interventional component may participate in an observational component which will recruit alongside the main study (max 30 patients). These patients will be monitored to record their treatments and outcomes and they will also have the option of contributing samples for biobanking over a 6 month period. No direct comparison will be made between the two arms in terms of outcome measures.

# 4. ELIGIBILITY

# 4.1 Inclusion Criteria

- Interventional component:
- Age ≥16 years old
- A prior diagnosis of Essential Thrombocythaemia (ET), Polycythaemia Vera (PV) or Myelofibrosis (MF) with one of the following:
  - 10-19% bone marrow blasts with or without dysplastic changes (MPN-AP) at baseline
  - ≥20% bone marrow blasts (MPN-BP) at baseline
- In need of treatment in the opinion of the investigator
- Eastern Cooperative Oncology Group (ECOG) performance status 0-3
- Adequate liver and renal function, defined as:
  - o liver transaminases ≤3 × ULN (AST/SGOT or ALT/SGPT)
  - o bilirubin <4 x ULN (Patients with elevated bilirubin due to Gilbert's syndrome are eligible)
  - o GFR ≥40 ml/min
- Willingness to undergo and ability to tolerate assessments during the study including bone marrow assessments and symptom assessments using patient reported outcome instruments
- Able to give valid informed consent

# **Observational Component**

- Age ≥16 years old
- A prior diagnosis of ET, PV or MF with one of the following:
  - ≥10% blasts in blood or bone marrow with or without dysplastic changes (MPN-AP) at baseline
  - ≥20% blasts in blood or bone marrow (MPN-BP) at baseline
- Patients who are unwilling/unable to enter the interventional component and/or fail the interventional component entry criteria. This can include patients previously treated post transformation into MPN-AP/MPN-BP, or entered into studies with more aggressive therapy such as AML 17/19 as well as those receiving palliation only.
- Able to give valid informed consent

# 4.2 Exclusion Criteria

#### Interventional Component:

- Any co-morbidity that could limit compliance with the trial or any other condition (including laboratory abnormalities) that in the Investigators opinion will affect the patient's participation in this trial
- New York Heart Association Class II, III, or IV congestive heart failure

- On-going cardiac dysrhythmias of grade 3, QTc prolongation >480 ms, or other factors that increase the risk of QT interval prolongation (e.g. heart failure, hypokalemia defined as serum potassium <3.0 mEq/L, family history of long QT interval syndrome)

- Erythropoietic agent within 28 days prior to registration
- Thrombopoietic agent within 14 days prior to registration
- Potent CYP3A4 inhibitor within 7 days prior to registration
- Experimental treatment within 14 days prior to registration
- Previous treatment for MPN-AP or MPN-BP, including stem cell transplant and low intensity AML chemotherapy
- Previously received 5-azacitidine. Ruxolitinib can be taken up until study entry at the pre-study dose. Hydroxycarbamide prescribed prior to study entry must be stopped before the first scheduled day of trial treatment
- Known contraindications to receiving 5-azacitidine or ruxolitinib
- Active infection ≥ grade 3 (CTCAE criteria) at trial entry
- Known HIV seropositivity
- Known to have active hepatitis A, B, or C
- Women who are pregnant or lactating. Patients of childbearing potential must have a negative pregnancy test prior to study entry
- Patients and partners of childbearing potential not willing to use effective contraception for the duration of the study treatment and for three months after the last dose

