# 7.10 Supportive Treatment

#### **Interventional Component**

As ruxolitinib is associated with the development and reactivation of bacterial, fungal and viral infections, patients should be monitored for symptoms at protocol visits and use of antibiotic, antiviral and antifungal prophylaxis are advised as per local protocols. Special attention should be paid to the possibility of reactivation of tuberculosis and Herpes Zoster. Patients should be educated about the early symptoms of Herpes Zoster to enable them to notify the research team and receive treatment as soon as possible.

Patients may also receive treatment with G-CSF/GM-CSF and / or blood transfusions (red blood cells and platelets) as applicable. EPO and TPO are prohibited throughout the trial.

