#### 12.2.1.2 Secondary outcome measures

The following will be analysed for patients in the interventional component:

- Best response following 3 and 6 cycles of treatment. Response will be assessed according to the following criteria:
  - Proposed criteria for response assessment in patients treated in clinical trials for MPNs in blast phase (MPN-BP): Formal recommendations from the post-MPN acute myeloid leukaemia consortium" (for patients with ≥20% bone marrow blasts at baseline)[1]
  - International Working Group (IWG) response criteria in myelodysplasia (for patients with <20% bone marrow blasts at baseline)[2]

In order to assess disease response, bone marrow, peripheral blood and spleen/liver assessments should be performed during days 22-25 of cycle 3 and cycle 6.

• Achievement of RBC transfusion independence after completion of cycles 3 and 6 compared to baseline.

RBC transfusion dependence is defined as transfusion of  $\geq 2$  RBC units in the 8 weeks prior to registration at baseline, and as transfusion of  $\geq 2$  RBC units in the 8 weeks prior to cycle 3-day 28 or cycle 6-day 28 for subsequent assessments.

• Achievement of platelet transfusion independence after completion of cycles 3 and 6 compared to baseline.

Platelet transfusion dependence is defined as transfusion of  $\geq 1$  platelet units in the 4 weeks prior to registration at baseline, and as transfusion of  $\geq 1$  platelet units in the 4 weeks prior to cycle 3-day 28 or cycle 6-day 28 for subsequent assessments.

- Change in the proportion of RBC or platelet transfusion-dependent patients after completion of cycles 3 and 6 compared to baseline as defined above.
- Change in palpable splenomegaly or hepatomegaly after completion of cycles 3 and 6 compared to baseline

Size of palpable spleens will be measured below the left costal margin and reported in cm Size of palpable livers will be measured below the right costal margin and reported in cm

- Duration of Complete Response (CR) or Partial Response (PR) according to established criteria
   [1] [2]
- 12 months Progression-free survival (PFS)
- 12 months Leukaemia-free survival (LFS)

- 12 months Overall survival (OS)
- Duration of trial treatment
- Mean change in haemoglobin level from baseline to end of cycles 3 and 6 (cycle 3-day 22-25 or cycle 6-day 22-25)
- Mean change in platelet count from baseline to end of cycles 3 and 6 6 (cycle 3-day 22-25 or cycle 6-day 22-25)

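### The agent-free period before registration covers only half of each baseline transfusion window, so in patients who used an effective agent earlier an unchanged need can look like worsening

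*Protocol*

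**What the plan says.** Three parts of the protocol meet here.

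- **Eligibility (4.2, interventional component).** The exclusions are "Erythropoietic agent within 28 days prior to registration" and "Thrombopoietic agent within 14 days prior to registration". Earlier use is allowed.
- **Outcome definitions (12.2.1.2).** Red cell dependence at baseline is 2 or more "RBC units in the 8 weeks prior to registration at baseline". Platelet dependence at baseline is 1 or more "platelet units in the 4 weeks prior to registration at baseline". On trial the same thresholds apply to "RBC units in the 8 weeks prior to cycle 3-day 28 or cycle 6-day 28 for subsequent assessments" and "platelet units in the 4 weeks prior to cycle 3-day 28 or cycle 6-day 28 for subsequent assessments". The listed outcomes include independence from red cell transfusion, independence from platelet transfusion, and "Change in the proportion of RBC or platelet transfusion-dependent patients after completion of cycles 3 and 6 compared to baseline".
- **Supportive treatment (7.10).** "EPO and TPO are prohibited throughout the trial".

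Nothing in 12.2.1.2 separates patients who used one of these agents inside the baseline window from those who did not.

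**The concern.** Each of these outcomes sets a patient's transfusion count before registration against a count on trial. That is informative about the combination only if the two windows differ mainly in trial treatment. For a patient who had an erythropoietic agent 29 to 56 days before registration, or a thrombopoietic agent 15 to 28 days before, they also differ in an agent given to reduce transfusion need: present in part of the baseline window, absent by rule from the follow-up window.

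If the agent worked, the baseline count is too low. A patient whose underlying need has not changed may then be classed as independent at baseline and dependent at cycle 3 or 6. The same patient is also no longer among those who could be seen to achieve independence. The error would count against the combination. The interventional component has a single arm, and section 3.2 rules out a direct comparison with the observational component, so no control group would reveal the artefact.

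**Working it through.** The protocol attaches no power or precision figure to the transfusion outcomes, so there is no stated figure to reproduce. The check is window arithmetic followed by an illustration.

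**Step 1: exposed share of the baseline window** = (window - agent-free period) / window, from 12.2.1.2 and 4.2.

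- Red cells: (56 - 28) / 56 = 50%.
- Platelets: (28 - 14) / 28 = 50%.

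**Step 2: exposed share of the follow-up window.** Cycles last 28 days, so cycle 3 day 28 is at least 84 days after treatment starts. Counting back 56 days still leaves 84 - 56 = 28 days on trial before the red cell window opens. The platelet window and both cycle 6 windows open later still. All lie inside the ban in 7.10, so the share is 0%.

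**Step 3: effect on one exposed patient with unchanged need.** Assumptions not in the protocol: transfused units follow a Poisson distribution; off-agent need is λ units per window; the agent covers the whole early half and cuts need there by a fraction r. The baseline mean is then λ(1 - r/2) and the on-trial mean is λ.

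- Red cells: P(dependent) = P(X ≥ 2) = 1 - e^(-m)(1 + m), where m is the mean.
- Platelets: P(dependent) = P(X ≥ 1) = 1 - e^(-m).

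For λ = 2 red cell units and r = 50%, the baseline mean is 1.5: 1 - e^(-1.5) × 2.5 = 0.442. On trial: 1 - e^(-2) × 3 = 0.594. The difference is 15 points.

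| Need off agent | On trial | Baseline, r = 25% | r = 50% | r = 100% | Apparent worsening (points) |
|---|---|---|---|---|---|
| 2 red cell units / 8 weeks | 59% | 52% | 44% | 26% | 7, 15, 33 |
| 4 red cell units / 8 weeks | 91% | 86% | 80% | 59% | 4, 11, 31 |
| 6 red cell units / 8 weeks | 98% | 97% | 94% | 80% | 1.5, 4, 18 |
| 1 platelet unit / 4 weeks | 63% | 58% | 53% | 39% | 5, 10, 24 |

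With r = 0 the shift is zero. It also shrinks as need rises well above the threshold.

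**Step 4: effect on the cohort proportion** = shift per exposed patient × exposed patients / 34, where 34 is the maximum sample size. Assume 1 to 5 exposed patients and 2 red cell units per 8 weeks.

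- Low end: 7.2 × 1/34 = 0.2 points.
- High end: 33 × 5/34 = 4.9 points.

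**The case against.** **The mismatch may affect nobody.** The protocol says neither how many patients will have used such an agent nor how well it worked. At 25-50% reductions and 1-5 exposed patients, the cohort shift is 7.2 × 1/34 = 0.2 to 15.2 × 5/34 = 2.2 points. The standard error of a 50% proportion in 34 patients is √(0.25/34) = 8.6 points. This stands as a limit on size. It does not remove the direction of the error.

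**The outcomes are secondary and descriptive**, and the MTD rests on cycle 1 DLTs. Because the error runs against the combination, it cannot create a false claim of benefit. This also stands.

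**A handling rule could sit in the SAP**, which is not available here. But the protocol itself fixes both windows and the comparison between them, so the mismatch is in its own definitions.

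**Other background treatment changes at entry too.** Prior ruxolitinib moves to the study dose and hydroxycarbamide stops. Aligning one agent class will not make the windows fully comparable, but this one is specific and easily handled.

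Three stronger readings are tempting and not supported:

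- A reader might infer that an unchanged need will look like worsening in general. It can do so only in patients exposed in the early half of the window whose agent reduced transfusions.
- A reader might take shifts above 30 points per patient as typical. They assume that the agent abolished transfusion altogether, which is an upper bound.
- A reader might infer from the schedule that earlier use cannot be recovered, because baseline concomitant medication is marked in the 7-day column. That column shows when the assessment is done. The transfusion assessment is marked in the same column, yet section 7.5.9 has it look back 8 weeks, and section 7.5.1 records previous treatments. What can be said is that the protocol does not expressly ask for a last-use date for these agents.

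Separately, the cytopenia text in section 7.8.2 allows growth factor support without naming agents, whereas 7.10 names G-CSF/GM-CSF and bans EPO and TPO. The two passages must be reconciled. The explicit ban is what the follow-up windows are read against here.

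**Conclusion.** The concern holds in a limited form. The 50% overlap at baseline and the zero overlap at follow-up come directly from the protocol and need no assumption. For a patient who used an effective agent in the early half of the window, baseline dependence can be understated, an unchanged need can look like worsening, and the patient may be lost from those able to achieve independence. The size rests wholly on assumptions: constant Poisson need, a 25-100% agent effect, and 1 to 5 exposed patients of 34. On these, the shift is about 7-33 points per exposed patient at 2 red cell units per 8 weeks, and about 0.2-5 points on the cohort proportion. With no exposure or no agent effect it is zero. Three secondary outcomes are touched. The eligibility criteria are not shown to be wrong.

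**What to change.** Leave the eligibility criteria unchanged.

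1. **Baseline record.** Ask for the date of last erythropoietic agent over the 8 weeks before registration and of last thrombopoietic agent over the 4 weeks before, matching the look-back of the two transfusion windows.
2. **Section 12.2.1.2.** Keep the summary of all patients, in line with section 12.3, which reports on everyone recruited. Add a prespecified summary that leaves out patients exposed to an erythropoietic agent within 8 weeks from the red cell outcomes, and those exposed to a thrombopoietic agent within 4 weeks from the platelet outcomes. List those patients separately.

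In the added summary the exposed share of the baseline window falls from up to 50% to 0%, and the illustrated shift falls to zero apart from any carry-over from still earlier use. Simply dropping exposed patients would be a poorer choice: it departs from all-patient reporting and thins a cohort of at most 34.

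The cost is one date field, one extra summary, and a slightly smaller n in that summary: 29 to 33 instead of 34 if 1 to 5 patients were exposed.

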#### **Observational Component:**

No Exclusions planned.

# 5. SCREENING AND CONSENT

# 5.1 Screening

Investigators will be expected to maintain a Screening Log of all potential study candidates. This Log will include limited information about the potential candidate (e.g. date of birth and gender), the date and outcome of the screening process (e.g. enrolled into study, reason for ineligibility, or refused to participate).

For patients who appear to meet the criteria for participation in the study, the Investigator will provide information to allow them to make an informed decision regarding their participation. If informed consent is given (see section 5.2), the Investigator will conduct a full screening evaluation to ensure that the patient satisfies all inclusion and exclusion criteria. A patient who gives written informed consent and who satisfies all the inclusion and exclusion criteria may be registered onto the study. Note that assessments conducted as standard of care do not require informed consent and may be provided as screening data if conducted within the stipulated number of weeks prior to registration. Assessments required in screening are listed in the schedule of assessments and detailed in section 7.5 for the Interventional component and 7.6 for the Observational component.

# 5.2 Informed Consent

It is the responsibility of the Investigator to obtain written informed consent for each patient prior to performing any trial related procedure. Two Patient Information Sheets are provided to facilitate this process, one for the Interventional component and one for the Observational Component. Investigators must ensure that they adequately explain the relevant aims, trial treatments (if applicable), anticipated benefits and potential hazards of taking part in either component to the patient. The Investigator should also stress that the patient is completely free to refuse to take part or withdraw from the trial at any time. The patient should be given ample time (e.g. 24 hours) to read the Patient Information Sheet and to discuss their participation with others outside of the site research team. The patient must be given an opportunity to ask questions which should be answered to their satisfaction. The right of the patient to refuse to participate in the trial without giving a reason must be respected.

If the patient expresses an interest in participating in the trial they should be asked to sign and date the latest version of the relevant Informed Consent Form. The Investigator must then sign and date the form. A copy of the Informed Consent Form should be given to the patient, a copy should be filed in the hospital notes, and the original placed in the Investigator Site File (ISF). Once the patient is entered into the trial the patient's trial number should be entered on the Informed Consent Form maintained in the ISF. In addition, if the patient has given explicit consent a copy of the signed Informed Consent Form must be sent in the post to the Trials Office for review.

Details of the informed consent discussions should be recorded in the patient's medical notes, this should include date of, and information regarding, the initial discussion, the date consent was given, with the name of the trial and the version number of the Patient Information Sheet and Informed Consent Form. Throughout the trial the patient should have the opportunity to ask questions about the trial and any new information that may be relevant to the patient's continued participation should be shared with them in a timely manner. On occasion it may be necessary to re-consent the patient in which case the process above should be followed and the patient's right to withdraw from the trial respected. Patients are permitted to re-consent at the same visit that new information is provided if they wish to do so.

To avoid the need for repeat sampling, Investigators may collect and send baseline research bone marrow samples to the Central Laboratory at the same time as local diagnostic procedures are performed. Patients must consent to this on the 'Research Tissue Consent Form' provided by the Trials Office or using a standard NHS consent form for investigations or treatment (provided that this permits the collection, storage and transfer of material for research purposes). The Central Laboratory will process and store the sample but no investigations will be performed until the patient consents to the PHAZAR trial agreeing to the collection, storage and analysis of samples. Stored samples may also be used for future ethically approved medical research if the patient gives explicit consent for this purpose.

Electronic copies of the Patient Information Sheet and Informed Consent Form are available from the Trials Office and should be printed or photocopied onto the headed paper of the local institution.

Details of all patients approached about the trial should be recorded on the Patient Screening/Enrolment Log and with the patient's prior consent their General Practitioner (GP) should also be informed that they are taking part in the trial. A GP Letter is provided electronically for this purpose.

